10.3.2 Secondary Outcome Measurements

We will assess secondary outcomes including live birth, time to pregnancy, pregnancy loss rate [including ectopics and Pregnancies of Unknown Location (PULs)], multiple pregnancy rate, pregnancy complication rate including development of gestational hypertension and diabetes, mode of delivery, birth weight, neonatal complication rate, predictive factors for response including DNA polymorphisms, salivary biomarkers of stress, quality of life, and cost effectiveness. Additionally we will be examining changes in the microbiome and association with outcomes.

10.4 Sample Size and Accruals

10.4.1 Sample Size and Power Calculations

Estimates used for the power calculation are based on our experience from the OWL PCOS and AMIGOS trials as provided in the preliminary data section. The primary outcome for this trial is a good birth outcome defined as an infant (singleton or twin) born at ≥ 37 weeks between 2500 and 4000g without a major congenital anomaly. We will examine the cumulative rates between groups. We anticipate the proportion of good birth outcomes to be 0.25 in the standard lifestyle intervention (physical activity and weight maintenance) arm and 0.40 in the Intensive lifestyle modification arm. We anticipate that there will be an increased proportion of good birth outcomes in each group beyond our preliminary data, as we will not actively prevent pregnancy during the lifestyle intervention; therefore, they will have an additional 16 weeks to conceive prior to initiating empiric treatment. A sample size of 190 per treatment arm will provide 80% power to detect a 0.15 absolute difference in the proportion of good perinatal births (0.25 in the standard lifestyle modification and 0.40 in the intensive group using a two-sided test having a significance level of 0.05. Although the randomization is stratified by two factors (recruitment site and BMI status), this factor was not taken into consideration for the power analysis to be conservative because accounting for the correlation of these covariates with the outcome would simply increase the precision, and hence, increase the power. The sample size has been inflated to a total of 380 participants to allow for a dropout rate of 20%. We believe this 20% dropout rate is a reasonable estimate based on current experience in our PPCOS I, PPCOS II, OWL PCOS, and AMIGOS trials. The table below summarizes other possible sample size scenarios having a 0.15 absolute difference in the proportion of good birth outcomes between the two treatment arms, all of which we would have excellent power to detect (**Table 11**).

Table 11: Sample size scenarios based on varying assumptions

Standard Lifestyle Modification: Physical Activity Arm having a Good Birth Outcome	Intensive Lifestyle Modification Weight Loss and Physical Activity Arm: Proportion having a Good Birth Outcome		Significance Level (alpha)	Power (%)	N per Arm (0% Dropout)	N per Arm (20% Dropout)
0.15	0.30		0.05	80	121	152
			0.05	90	161	202
0.20	0.35		0.05	80	138	173
			0.05	90	185	232
0.25	0.40		0.05	80	152	190
			0.05	90	203	254

10.4.2 Accrual

A total of 2.6 years will be required to complete the study after start up; 15 month enrollment period (based on 2 subjects per site/month x 13 sites), 7 month treatment period (4 months lifestyle pretreatment and 3 months ovarian stimulation/IUI), with 9 month additional observation to determine pregnancy outcomes.

10.5 Data Monitoring

There will be no pre-determined stopping rules and no interim analysis.

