4.1.1 Treatment Design

This will be a two-arm, multi-center, prospective randomized trial of two types of lifestyle modification in obese women with unexplained infertility who will be randomized to either an intensive lifestyle modification with weight loss and increased physical activity or a standard lifestyle modification consisting of increased physical activity for 16 weeks prior to initiating infertility treatment with an oral drug, clomiphene, to stimulate follicular development followed by intrauterine insemination (IUI). The lifestyle modifications will be open label with adequate allocation concealment and the randomization ratio will be equal between modifications (1:1).

The appropriate study candidates will be recruited from the main sites of the Reproductive Medicine Network and their ancillary partners. Recruited subjects will meet the inclusion and exclusion criteria detailed below. Monitoring of this trial at all sites will be conducted by the RMN Data Coordination Center, with progress reports provided to the RMN Data and Safety Monitoring Board (DSMB) no less than every three months in order to review trial progress and subject safety.

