10.8 Reporting

Administrative Reports will be prepared by the DCC, and they include monthly and quarterly reports to the RMN on accrual, data quality and study compliance and reports presented in the packet produced for each Steering Committee and DSMB. Statistical reports include reports to the SC and AB from the data analysis, and special reports for scientific manuscripts.

Statistical Reports will be generated in SAS. Reports are provided for DSMB reviews, and for final analysis of study results in preparation for scientific publications. The content of the interim reports will be very complete, and will serve as the template for the final report of each study, which in turn will form the basis of the publication of the results. Our proposed reports to the DSMB would include the following: a protocol description and history; accrual rates; site performance in terms of accrual; eligibility; protocol violations; data accuracy and minority representation; patient characteristics by treatment and site; and the rate of adverse experiences.

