- I don't use sunscreen

12. How often do you spend time in the sun or in a tanning bed/booth in order to get a tan or to feel good?

- Never
- Rarely
- Sometimes
- Often
- Always

13. Have you been tan in the last 12 months?

- Yes
- No

14. In the **SUMMER** (June, July, August), on average, how many hours per day are you **outside** between 10am and 4pm?

	Less than 1 hour	1 hour	2 hours	3 hours	4 hours	5 hours	6 hours
On WEEKDAYS (Monday-Friday)							
On WEEKENDS (Saturday and Sunday)							

15. In **NON-SUMMER** months (September to May), on average, how many hours per day are you **outside** between 10am and 4pm?

	Less than 1 hour	1 hour	2 hours	3 hours	4 hours	5 hours	6 hours
On WEEKDAYS (Monday-Friday)							
On WEEKENDS (Saturday and Sunday)							

32 Appendix P: DSMB Charter

Improving Reproductive Fitness through Pretreatment with Lifestyle Modification in Obese Women with Unexplained Infertility: (FIT-PLESE FEMALE)

DATA AND SAFETY MONITORING BOARD (DSMB) CHARTER

1. Purpose and Responsibilities of the DSMB

The members of the Data and Safety Monitoring Board (DSMB) identified in this Charter for the FIT-PLESE Female study are responsible for safeguarding the interests of study participants, assessing the safety and efficacy of all study procedures, and shall monitor the overall conduct of the FIT-PLESE Female trial. This Committee will serve as an independent advisory group to the Director of NICHD, and is required to provide recommendations about starting, continuing, and stopping the FIT-PLESE Female study.

This Committee is responsible for identifying mechanisms to complete various tasks that will impact the safety and efficacy of all study procedures, and overall conduct. The table below identifies the key areas where oversight is necessary and the ways in which the Committee for the FIT-PLESE Female study will complete those tasks.

Basic Responsibility of DSMB	Method DSMB for FIT-PLESE Female will use to complete task
Familiarize themselves with the study protocol	
· Review study protocols and informed consent forms.

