Monitor adverse events	
· Adverse Event: Review quarterly progress reports prepared by the DCC on behalf of RMN.· Serious Adverse Events: Review report submitted by the DCC on behalf of RMN within one week of the event if life threatening or fatal, or within two weeks otherwise. The DSMB will submit a report of their review to the NICHD Committee Coordinator within 7 business days if the SAE is life threatening or fatal, or within two weeks otherwise.
Monitor data quality	
· Conduct interim evaluations of the data.
Oversee participant recruitment and enrollment	
· Review interim progress reports prepared by the DCC on behalf of RMN.
Develop an understanding of the Study's risks and benefits	
· Review study protocols and related literatures.· Review interim reports of subject accrual and outcome measures provided by the DCC.

	
 · Assess the need to perform further in-depth evaluation of the benefits and risks of the study after reviewing each report.
Ensure the proper reporting occurs	
 · Review and approve the meeting and reporting schedule listed in Section 5 of this DSMB charter.

2. Contacts

NICHD

[name], Program Officer/Committee Coordinator
 [name], MPH, Project Scientist

Data Coordination Center (DCC)

[name], DCC Principal Investigator
 [name], DCC Data Manager

The Data Manager at the DCC will prepare and review the DSMB reports prior to submission to the DSMB, and will not be blind to treatment condition.

Lead Investigator

[name]

3. DSMB Members, Organizational Chart, & Communications

Members

[figure not shown]
The DSMB for the FIT-PLESE Female study is comprised of the members listed in the table below. In addition, their high level roles and responsibilities are identified in the table.

Name of Member	Role on DSMB	High Level Responsibilities
[name]	Chair of DSMB Voting member	
 · Chair the DSMB discussion and prepare written recommendations to NICHD. · Ensure the safety of study subjects, the integrity of the research data. · Provide NICHD with advice on the ethical and safe progression of studies conducted in the RMN. · Advises on research design issues, data quality and analysis, and research participant protection for each prospective and on-going study.

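### Does the DSMB Charter's review of outcomes and benefit contradict the protocol's statement that there is no interim analysis?

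*Combined protocol and SAP*

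**What the plan says.** **Protocol.** Section 10.5 is categorical: "There will be no pre-determined stopping rules and no interim analysis". Section 4.1.1 has progress reports go to the DSMB "no less than every three months in order to review trial progress and subject safety". Section 10.8 describes their content: "Our proposed reports to the DSMB would include the following: a protocol description and history; accrual rates". The list goes on to site performance, eligibility, violations, data accuracy, minority representation, patient characteristics and adverse experiences, and names no outcome. The same section says what reports would include and calls the interim reports very complete, so the list is not a closed one. Section 10.7 says the DSMB will carry out interim evaluations of the data as the protocols outline. That sentence directly follows one on monitoring data quality, adherence and adverse events. The sample size in section 10.4.1 is computed "using a two-sided test having a significance level of 0.05".

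**DSMB Charter (Appendix P).** Section 1 makes the board responsible for "assessing the safety and efficacy of all study procedures" and says it "is required to provide recommendations about starting, continuing, and stopping the FIT-PLESE Female study". In the table of responsibilities, the row on understanding risks and benefits has the board read the protocols and literature, then "Review interim reports of subject accrual and outcome measures provided by the DCC", and "Assess the need to perform further in-depth evaluation of the benefits and risks of the study after reviewing each report". Section 6 has all summaries presented blinded unless the Chair specifies otherwise. Section 7 lists a primary-outcome update in both the brief and the full report, and so in all 16 scheduled reports.

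**The concern.** Read together, the two texts seem to give the board different jobs. The protocol describes a board that watches conduct and safety. The Charter describes one that also considers efficacy, sees the primary outcome each time, asks after each report whether benefit and risk need a closer look, and can recommend stopping. A closer look at benefit by arm would be an interim analysis in all but name, and no boundary, alpha spending or decision rule is given for it.

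At stake would be the type I error of the final test. If accumulating good birth outcome data were compared by arm, judged at 0.05 each time, and allowed to end the trial for benefit, the overall false-positive rate would exceed 0.05. A reader of the final report could also ask whether the final test was really the only one.

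**Working it through.** **1. The plan's own figure.** Inputs from section 10.4.1: proportions 0.25 and 0.40, two-sided alpha 0.05, power 0.80, dropout 20%. With pooled variance and no continuity correction, the mean proportion is 0.325 and

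n = [1.960 × √(2 × 0.325 × 0.675) + 0.8416 × √(0.25 × 0.75 + 0.40 × 0.60)]² / 0.15²

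= [1.2982 + 0.5503]² / 0.0225 = 3.417 / 0.0225 = 151.9, so 152 per arm.

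Allowing for dropout, 152 / 0.80 = 190 per arm, or 380 in total. The other rows of Table 11 also reproduce. This is a single-look design with no allowance for repeated testing, as section 10.5 implies. Power at 152 per arm is 0.800.

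**2. What would have to be true for type I error to move.** Looking at data does not by itself change the error rate of the final test. Three things are needed together: the outcome is shown by arm, the difference is judged against a threshold, and crossing it can end the trial with a claim of benefit.

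- *Shown by arm.* The update in Charter section 7 is not said to be comparative. Section 6 makes blinding the default. The Chair may lift it, and the text does not say whether blinded means pooled or coded arms, so arm-level display is possible but not planned.
- *Judged against a threshold.* No supplied passage names a test, p-value or boundary for an interim look. The Charter's own row on interim evaluations concerns data quality, which fits the context of the similar sentence in section 10.7.
- *Able to stop for benefit.* Section 10.5 excludes pre-determined stopping rules. Section 10.7 gives subject welfare and scientific integrity as the grounds for recommending protocol modifications, and section 12.3 ties discontinuation by the IRB or agencies to protecting subjects. Neither mentions efficacy. A stop for safety with no efficacy claim removes chances to declare benefit and adds none.

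The second and third conditions are absent from the text, so the final test keeps its level of 0.05.

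**3. Conditional size, if all three held.** Assumptions: reports every 3 months, uniform accrual over 15 months, the outcome known at a fixed lag after randomization, and each look judged at |Z| > 1.96. The information fraction at month t is (t − lag)/15. Each type I error below is from 400,000 simulated null trials.

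| Scenario | Information fractions | Overall type I error |
|---|---|---|
| Final test only | 1 | 0.050 |
| One equally spaced look plus final | 0.5, 1 | 0.083 |
| Lag 12 months | 0.2, 0.4, 0.6, 0.8, 1 | 0.141 |
| Lag 7 or 16 months | 0.133, 0.333, 0.533, 0.733, 0.933, 1 | 0.157 |

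The lags run from the end of the 7-month treatment period to 7 + 9 = 16 months. Even then the size depends on the threshold. With interim looks held to |Z| > 3.29 and the final at 1.96, the overall rate was about 0.050 to 0.053 for up to 16 equally spaced analyses. These figures show what unplanned testing could cost. They do not describe this plan.

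**The case for a change.** The strongest case for a change runs as follows. The Charter is the board's working document, and no supplied passage says which text prevails. Blinding is only a default. Benefit cannot be evaluated in depth without comparing arms. The predecessor trial described in section 3.6 was also open label, and it stopped enrolment at 149 of a planned 246 after outcomes were tracked and its DSMB advised it. A sentence now would be cheap, and would carry more weight than one written after outcome data exist.

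Part of this stands. The wording differs, and section 10.7 shows that the protocol is itself not uniform on interim evaluations. The rest does not lead to a change. The Charter asks the board to decide whether a further evaluation is needed; it does not schedule one. Efficacy is a general remit and not an item in each report. A board that may recommend stopping to protect participants has to be able to weigh benefit against harm, and that is compatible with making no efficacy test. The predecessor was a separate three-arm trial with its own board. Its text does not say whether enrolment stopped for benefit or futility, so it shows nothing about how this Charter would be used. An added sentence would record what section 10.5 already implies, and a formal boundary would serve testing that nobody has proposed.

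**Conclusion.** The concern does not call for a change. The protocol and Charter describe the board's reports in different words, but the analytic instruction is clear: no interim analysis, and one final two-sided test at 0.05. A trial statistician would treat the primary-outcome update as descriptive and leave the final alpha untouched. Sample size (152 evaluable, 190 randomized per arm), power (0.800) and type I error (0.05) are unaffected, so aligning the wording would be housekeeping that alters no result.

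This rests on two assumptions: that section 10.5 is followed, and that no formal comparison by arm of good birth outcome is used to stop the trial for benefit. Part of the Charter, between its sections 3 and 5, was not in the copy reviewed. If that part provides for an efficacy stop on arm-level data, the conclusion would need to be revisited. Nothing in the supplied text suggests that it does.

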10.6 Study Monitoring

A monitoring plan that satisfies the ICH/GCP guidelines for clinical monitoring will be used. A Project Manager from the DCC will lead this effort, and report findings to the DCC PI. The Project Manager will have full knowledge of the study protocol, Manuals of Procedures, and is familiar with the database system and is trained to review patient charts. The Project Manager will be responsible for training and supervising other personnel.

Once personnel at participating site are trained to recruit patients, the Project Manager will be sent to the site to help initiate the study according to the study protocol, and to ensure that the clinical site meets the scientific, clinical, and regulatory requirements. For example, the Project Manager will review all signed and dated forms (such as financial disclosure forms), the curriculum vitae and certifications of the investigators and personnel, CRF training, and the written IRB approval of the protocol and consent form.

The on-site monitor will return to the clinical site after a defined number of patients are recruited (can be as early as the recruitment of the 2nd patient) or a certain time period has passed, depending on the duration of the protocol execution. The schedule of visits will be discussed and agreed in the Steering Committee and we anticipate that the Project Manager will visit each participating site at least once.

During the site visit, the clinical sites should provide to the monitor a space and access to all relevant records including medical records and regulatory binders, and there would be immediate verbal feedback provided to the site after original source documents are compared to entries in the CRF. The clinical sites must agree to cooperate with the monitor to ensure that any problems detected in the course of these monitoring visits are resolved. The on-site monitor will conduct an audit of a random sample of entered information against the source documents, a review of all regulatory documents, a review of all informed consents, and a review of all pharmacy logs. The clinical site PI and coordinator should be available to meet the monitor during the visit. The monitor will review electronic data from all sites, providing a method for identifying systematic errors or problems.

To assure Good Clinical/Laboratory Practice, the monitor will control adherence to the protocol at the clinical sites and evaluate the competence of the personnel at the clinical sites including the ability to obtain written informed consents and record data correctly. The monitor will inform the DCC PI, the Steering Committee, and NICHD regarding problems relating to facilities, technical equipment, or medical staff. A thorough written report will follow each site-visit and will include a detailed itemization of discrepancies and items requiring follow-up or reconciliation. This report will also be forwarded to the NICHD Research Scientist for review. The monitor will be responsible for maintaining regular contacts between the investigators in the clinical sites and the RMN. When the study ends, the monitor will also visit the clinical site to provide assistance for close-out.

10.7 Data and Safety Monitoring Board

The NICHD has established a DSMB to review and interpret data generated from RMN studies and to review protocols prior to their implementation. Its primary objectives are to ensure the safety of study subjects, the integrity of the research data and to provide NICHD with advice on

the ethical and safe progression of studies conducted in the RMN. The DSMB advises on research design issues, data quality and analysis, and research participant protections for each prospective and on-going study. A copy of the DSMB Charter can be found in the appendix.

The DSMB members are appointed by the Director of NICHD in accordance with established NIH and NICHD policies. DSMB members are experts in and represent the following fields: biostatistics, epidemiology, infertility, gynecology, andrology and ethics. The NICHD Committee Coordinator is responsible for scheduling regular committee meetings, recording all meeting minutes and summarizing the committee recommendations for the Steering Committee and NICHD. Steering Committee members are prohibited from attending closed sessions of the DSMB. Open sessions may be attended by Steering Committee members or Chairperson when requested by NICHD and the DSMB.

The DSMB meets regularly at a time and place of their choosing to review Network randomized trial protocols with respect to ethical and safety standards, monitors the safety of on-going clinical trials, monitors the integrity of the data with respect to original study design, and provides advice on study conduct. The DSMB periodically monitors data quality, including protocol adherence and adverse events. As outlined in the protocols, the DSMB will conduct interim evaluations of the data. It may recommend protocol modifications based on concern for subject welfare and scientific integrity.

10.8 Reporting

Administrative Reports will be prepared by the DCC, and they include monthly and quarterly reports to the RMN on accrual, data quality and study compliance and reports presented in the packet produced for each Steering Committee and DSMB. Statistical reports include reports to the SC and AB from the data analysis, and special reports for scientific manuscripts.

Statistical Reports will be generated in SAS. Reports are provided for DSMB reviews, and for final analysis of study results in preparation for scientific publications. The content of the interim reports will be very complete, and will serve as the template for the final report of each study, which in turn will form the basis of the publication of the results. Our proposed reports to the DSMB would include the following: a protocol description and history; accrual rates; site performance in terms of accrual; eligibility; protocol violations; data accuracy and minority representation; patient characteristics by treatment and site; and the rate of adverse experiences.

